7.0 EVALUATIONS/MATERIAL AND DATA TO BE ACCESSIONED

Timing of protocol therapy administration, response assessment studies, and surgical interventions are based on schedules derived from the experimental design or on established standards of care. Minor unavoidable departures (up to 72 hours) from protocol directed therapy and/or disease evaluations (and up to 1 week for surgery) for valid clinical, patient and family logistical, or facility, procedure and/or anesthesia scheduling issues are acceptable (except where explicitly prohibited within the protocol).

7.1 End of Therapy & Follow-up

STUDIES TO BE OBTAINED	End of Therapy
History	X
Physical exam with VS	X
Performance status	X
CBC, differential, platelets	X
Electrolytes including Ca ⁺⁺ , PO ₄ , Mg ⁺⁺	X
Creatinine, SGPT, bilirubin	X
Total protein/albumin	X
Tumor disease evaluation (see Section 16.0)	X

See COG Late Effects Guidelines for recommended post treatment follow-up:

<http://www.survivorshipguidelines.org/>

Note: Follow-up data must be submitted in accordance with the Case Report Forms (CRFs) schedule.

8.0 CRITERIA FOR REMOVAL FROM PROTOCOL THERAPY AND OFF STUDY CRITERIA

8.1 Criteria for Removal from Protocol Therapy

- a) Progressive disease.
- b) Unacceptable toxicity due to protocol therapy (see [Section 5.0](#)).
- c) Refusal of further protocol therapy by patient/parent/guardian.
- d) Completion of planned therapy.
- e) Physician determines it is in patient's best interest.
- f) Development of a second malignancy.
- g) Repeat eligibility studies (if required) are outside the parameters required for eligibility (see Section 3.2).
- h) Surgery or radiation performed on any site of measurable disease before the end of the 6th cycle.
- i) Failure to recover from surgery within 6 weeks.
- j) Pregnancy.

Patients who are off protocol therapy are to be followed until they meet the criteria for Off Study (see below). Follow-up data will be required unless patient is taken off study.

8.2 Off Study Criteria

- a) Death.
- b) Lost to follow-up.
- c) Patient enrollment onto another COG study with tumor therapeutic intent (eg, at recurrence).
- d) Withdrawal of consent for any further data submission.
- e) The fifth anniversary of the date the patient was enrolled on this study.

9.0 STATISTICAL CONSIDERATIONS

9.1 Sample Size and Study Duration

A review of enrollment on COG single-agent Phase 2 studies demonstrates that approximately 1.8 patients per month will potentially be eligible for AOST1521. A maximum of 29 outcome evaluable patients will be required for the evaluation of CDX-011 amongst patients without prior treatment with eribulin. Eribulin has not been used as a component of therapy for newly diagnosed patients in pediatric protocols and there has been only one COG study of that agent for patients with recurrent disease. As such, we expected no more than 15% of patients who are eligible for this study to have received eribulin as part of therapy prior to potential enrollment on this study. Providing for possible ineligible and inevaluable patients, the maximum enrollment will be 38 patients.

With these entry rates, the probability we will accrue at least 38 patients in 24 months is 80% and the corresponding probability for 30 months is in excess of 99%. The study will likely require 2 to 2.5 years to enroll sufficient patients. A maximum of 38 patients is anticipated.

9.2 Study Design

Feasibility Cohort: The first six (6) younger patients (< 18 years of age) who are evaluable for toxicity will be considered as the feasibility cohort. All such patients will be assigned to receive 1.9 mg/kg/dose. Enrollment to this cohort will not be segregated by prior treatment with eribulin. Study accrual will be suspended after the sixth patient is enrolled; enrollment of patients 18 years of age or older will continue regardless of the result in the feasibility cohort. If dose limiting toxicity (DLT) during the first cycle of therapy occurs in one or fewer evaluable patients then the trial accrual will proceed as outlined below. Patients who are enrolled in the toxicity cohort who receive the “feasible” dose of CDX-011 will be considered in the outcome evaluation rules presented below for the relevant patient stratum as it relates to prior eribulin exposure.

Patients will be enrolled in two stages. In the first stage, 19 disease control and RECIST response evaluable patients will be enrolled. Each patient will be evaluated for both outcome measures: (1) disease control success; and (2) RECIST response (CR or PR v. not CR or PR). The decision rule for the two stage study design is summarized as:

Stage	Number of Patients Enrolled in Stage	Cumulative Response Results	Decision
I	19	4 or fewer disease control successes	Terminate the trial with the conclusion that Glembatumumab

		and 1 or fewer RECIST responders	Vedotin is not associated with sufficient activity for further single agent investigation
		5 or more disease control success or 2 or more RECIST responders	Continue to stage II
II	10	8 or fewer disease control successes and 4 or fewer RECIST responders	Terminate the trial with the conclusion that Glembatumumab Vedotin is not associated with sufficient activity for further single agent investigation
		9 or more disease control successes or 5 or more RECIST responders	Terminate the trial with the conclusion that Glembatumumab Vedotin is associated with sufficient activity for further single agent investigation

Design Characteristics: Each patient enrolled will be evaluated for: (1) complete or partial response as defined by the RECIST criteria where the first evaluation of CR or PR is made at or before the end of the sixth cycle of study therapy (denoted as R below); or (2) stable disease after four months of therapy or at the end of the sixth cycle, whichever occurs first (denoted as S below). We will not be interested in promoting the agent for further investigation if the probability of response in any particular individual is less than or equal to 0.05 ($P(R) \leq 0.05$) and the probability of remaining analytic event free in any particular individual is less than or equal to 0.20 ($P(S) \leq 0.20$). We will be interested in promoting the agent for further investigation if the probability of response in any particular individual is at least 0.22 ($P(R) \geq 0.22$) **or** the probability of remaining analytic event free in any particular individual is at least 0.42 ($P(S) \geq 0.42$).

For the calculations below, it is assumed $\Pr(S|R) = 0.90$.

The statistical characteristics of this design are:

Probability of four month disease control	Probability of RECIST response	Probability of Stopping After Stage 1 (and concluding the drug is ineffective)	Probability of Concluding the Drug is Ineffective at the Conclusion of the Trial	Probability of Concluding the Drug is Effective at the Conclusion of the Trial
0.20	0.05	0.56	0.89	0.11
0.42	0.22	0.014	0.05	0.95
0.42	0.05	0.044	0.096	0.904
0.20	0.22	0.056	0.21	0.79

Prior Treatment with Eribulin: As noted in [Section 9.1](#), we expect no more than 15% of patients will have been treated with eribulin prior to enrollment on AOST1521. Patients will be evaluated for S and R as described above. Enrollment to this stratum will be terminated when we can determine there are sufficient patients to fully evaluate the efficacy of CDX-011 in the stratum of patients without prior eribulin therapy. If 19 patients with prior eribulin therapy are enrolled, the staged design described above for patients without prior eribulin therapy will be applied to this stratum.

9.3 Methods of Analysis for Pharmacokinetics (Aim 1.2.2)

Data from all patients who provide samples for pharmacokinetic analysis will be aggregated. The sample mean and variance of the AUC, clearance and half-life will be calculated. No formal statistical testing will be done.

Pharmacokinetic studies are mandatory for the first 6 evaluable patients 14 years of age or less who are enrolled at an institution which is a member of COG. Consent for pharmacokinetic studies for any patient greater than 14 years of age and less than or equal to 21 years of age who is enrolled at a COG member institution is optional. PK sampling will not be sought for patients who are older than 21 years of age at the time of enrollment.

9.4 Evaluability for Disease Control and Response

Which Patients will be Considered Evaluable for RECIST Response:

Any eligible patient who receives at least one dose of CDX-011 will be considered evaluable for response with the following exception: if a patient receives non-protocol anti-cancer therapy during the response evaluation period after the patient is considered as having a partial or complete response but prior to confirmation of this status by tumor imaging and before progressive disease is noted, the individual will be considered inevaluable for the response endpoint. Further, patients who stop CDX-011 after the 1st evaluation because of toxicities or death will be considered evaluable for the response evaluation and will be counted as non-responders for the response endpoint.

Which Patients Will Be Considered Evaluable for Disease Control Success:

Any eligible patient who receives at least one dose of CDX-011 will be considered evaluable for response with the following exception: if a patient receives non-protocol anti-cancer therapy during the first four months of therapy or first six cycles of therapy, whichever occurs first, is considered as having a partial or complete response but prior to confirmation of this status by tumor imaging and before progressive disease is noted, the individual will be considered inevaluable for the disease control success endpoint.

Which Patients Will be Considered a Disease Control Success:

Any patient who is evaluated free of all detectable disease (complete response) or is considered as having a partial response or is considered as having stable disease ('at least stable disease') after four months of therapy or at the end of the sixth cycle, whichever occurs first.

Which Patients Will be Considered Not a Disease Control Success:

Any evaluable patient who does not meet the criteria for disease control success (complete response, partial response or stable disease) will be considered to not have experienced disease control success.

In particular, any patient who dies because of treatment-related toxicity during the first six cycles of therapy and within the first four months since starting treatment will be

considered not to have experienced disease control success. Also, any patient who is eligible, receives one dose of CDX-011 and is lost to follow-up at (for example) the end of cycle 2 will be considered not a disease control success (complete response, partial response or stable disease).

Patients who are not evaluable for both disease control and response evaluation may be replaced for the purposes of the statistical rule.

9.5 **Evaluability for Toxicity**

Tolerability of CDX-011 - An eligible patient will be considered for toxicity monitoring if one of the following occurs: (1) complete one cycle of CDX-011 prior to receiving non-protocol anticancer therapy; (2) die on protocol therapy for a reason considered possibly, probably or likely related to CDX-011; or (3) are removed from protocol therapy because of an adverse experience possibly, probably or likely related to CDX-011. A toxicity-evaluable patient will be considered in the analysis during the interval from study enrollment until the termination of protocol therapy. A toxicity-evaluable patient will be considered to have experienced an excessive toxicity event if: (1) the patient dies on protocol therapy for a reason considered possibly, probably or likely related to; or (2) experiences a dose-limiting toxicity (DLT). DLTs will be as defined in [Section 5.1.1](#) of the protocol:

The analytic unit for monitoring for excessive toxicity will be the patient-cycle: Each cycle where the patient receives CDX-011 and does not receive non-protocol anticancer therapy will be considered in the analysis. If there is overwhelming evidence that the dose selected for this trial has a per-cycle-DLT probability of more than 30%, we will identify the regimen to the COG DSMC, Bone Tumor Committee leadership and CTEP as associated with a toxicity profile that may require modification of the regimen. We will use a Bayesian rule to monitor for excessive toxicity. We will assume a beta prior to distribution with $\alpha=0.6$ and $\beta=1.4$. If this posterior probability of the chance of DLT is at least 30% exceeds 80%, we will identify the regimen to the COG DSMC, Bone Tumor leadership and CTEP as associated with a toxicity profile that may require modification of the regimen.

9.6 **Estimation of Disease Control and RECIST Response Rates**

$P(R)$ and $P(S)$ for each cohort defined by prior eribulin exposure will be estimated using the maximum likelihood estimates, *viz.*,

$$P(R) \hat{=} \hat{p}_R = \frac{\text{Number of Patients Considered as PR or CR}}{\text{Number of Evaluable Patients in Cohort}};$$

$$P(S) \hat{=} \hat{p}_S = \frac{\text{Number of Patients With Disease Control at 4 Months}}{\text{Number of Evaluable Patients in Cohort}}$$

Confidence intervals will be constructed using the approximate normal distribution of each of the estimates and their asymptotic variances:

$$V(\hat{p}_R) \hat{=} \frac{\hat{p}_R(1-\hat{p}_R)}{\text{Number of Evaluable Patients in Cohort}};$$

$$V(\hat{p}_S) \hat{=} \frac{\hat{p}_S(1-\hat{p}_S)}{\text{Number of Evaluable Patients in Cohort}}$$

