4.2.2 Required Observations Prior to Cycle 1 and During All Cycles

All baseline studies must be performed prior to starting protocol therapy unless otherwise indicated below. For Cycle 1 only, observations a-f can be performed up to 7 days before the start of therapy and imaging studies may be obtained within 2 weeks prior to the start of therapy.

- a. Hx/PE/Wt /Ht. Prior to each cycle and on Day 8 of Cycle 1.
- b. CBC/diff/platelets. Prior to each cycle and on Day 8 of Cycle 1.
- c. Bilirubin & Creatinine. Prior to each cycle and on Day 8 of Cycle 1.
- d. Electrolytes, BUN, Ca⁺⁺, PO₄, Mg⁺⁺. Prior to each cycle and on Day 8 of Cycle 1.
- e. AST, ALT, albumin. Prior to each cycle and on Day 8 of Cycle 1.
- f. Neurologic evaluation. Prior to each cycle and on Day 8 of Cycle 1. Assess for NCI CTCAE > Grade 2 neuropathy.
- g. CT chest. Prior to Cycle 1 and following Cycles 2, 4, 6 and every 3rd cycle thereafter.
- h. Tumor disease evaluation. Prior to Cycle 1 and following Cycles 2, 4, 6, and every 3rd cycle thereafter. Evaluations should include CT or MRI of all lesions meeting eligibility criteria. Use the same imaging modality for all disease evaluations. Patients who had a RECIST response (CR or PR) at Cycle 6 imaging evaluation are required to have a confirmatory scan following Cycle 8. For patients who undergo a surgical resection following Cycle 6, either a CT scan or MRI post-surgery to establish a new baseline is strongly recommended prior to re-initiating CDX-011 therapy. See [Section 16.0](#) for details.
- i. ¹⁸FDG PET or Bone Scan. Prior to Cycle 1 and following Cycles 2, 4, 6, and every 3rd cycle thereafter. ¹⁸FDG PET or bone scan is required at baseline. ¹⁸FDG PET scan is an optional study, but if completed then a bone scan is not necessary. It is recommended to obtain MRI or CT scan of any lesion positive on bone or ¹⁸FDG PET scan. Bone or ¹⁸FDG PET scan is required to assess for new disease after Cycles 2, 4 and 6. Further bone scan or ¹⁸FDG PET should be completed as clinically indicated at investigator discretion. For consistency, investigators are encouraged to utilize the same modality used at baseline to follow positive lesions that are identified with ¹⁸FDG PET or bone scan. See [Section 16.0](#) for details.

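### Section 9.4 makes a treated patient inevaluable only after an observed CR/PR, so the denominators depend on outcome and the direction of the bias depends on how an unconfirmed response would otherwise count

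*Combined protocol and SAP*

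**What the plan says.** **Response (Section 9.4).** Any eligible patient with at least one dose is evaluable. The single exception is a patient already considered CR or PR who starts non-protocol anti-cancer therapy before imaging confirms the response and before progression; then "the individual will be considered inevaluable for the response endpoint". A patient who stops after the first evaluation because of toxicity or death stays in as a non-responder. Nothing is said of a patient with stable disease who starts other therapy, so that patient also stays in.

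**Disease control (Section 9.4).** A similar exception covers the first four months or six cycles. The sentence joins the therapy window to the unconfirmed CR/PR without a connecting word, so its condition has to be guessed. Treatment-related death in the window and loss to follow-up are scored as not a success.

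**Replacement and counting.** Section 9.4 ends: "Patients who are not evaluable for both disease control and response evaluation may be replaced for the purposes of the statistical rule". Section 9.2 says "In the first stage, 19 disease control and RECIST response evaluable patients will be enrolled". Section 9.6 divides by evaluable patients only.

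**Confirmation.** Section 10.2.3.3 makes best response depend on confirmation at four weeks or more. Its footnote applies this to non-randomized trials with response as primary endpoint, which describes this study. Under Section 4.2.2 item h, patients with a response at the Cycle 6 imaging "are required to have a confirmatory scan following Cycle 8".

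**A further rule.** Section 4.1 makes a patient inevaluable for disease control after surgery or radiation to measurable disease before the end of Cycle 6, whatever the response. Section 9.4 does not mention it.

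**The concern.** Take two patients who both start another agent. One has stable disease and stays in the response denominator as a non-responder. The other has shown a PR that is not yet confirmed and is removed. The outcome itself decides who is counted. Elsewhere in the same section the plan scores incomplete follow-up as failure, so this departure applies only to patients who showed a response.

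The situation is foreseeable. A first PR at the Cycle 6 scan waits two 21-day cycles, 2 × 21 = 42 days, for its confirming scan. The disease control time point has by then passed, so that patient is a disease control success and yet becomes inevaluable for response if other therapy starts in the gap. If the stages count only patients evaluable on both endpoints, the observed success can be dropped and the patient replaced.

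The decision rests on at most 29 patients and on boundaries of 5 responders or 9 disease control successes, so a few reclassified patients matter. The operating characteristics in Section 9.2 assume that every patient is classified.

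**Working it through.** **Inputs.** "A maximum of 29 outcome evaluable patients will be required" (Section 9.1), as 19 + 10. Continue after stage 1 with "5 or more disease control success or 2 or more RECIST responders"; declare activity at the end with "9 or more disease control successes or 5 or more RECIST responders" (Section 9.2). The drug is of no interest if "the probability of response in any particular individual is less than or equal to 0.05" and P(S) is at most 0.20; the alternatives are 0.22 and 0.42, with Pr(S|R) = 0.90 assumed (Section 9.2). The share of affected patients is not documented. I assume m = 1, 2 or 3 per 29, or a share f of responders.

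**Step 1: reproduce the plan.** Each patient falls in one of four cells: S and R = 0.9·P(R); S only = P(S) − 0.9·P(R); R only = 0.1·P(R); neither = the remainder. Exact enumeration of both stages gives:

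| P(S), P(R) | Plan: stop stage 1 / ineffective / effective | Recomputed |
|---|---|---|
| 0.20, 0.05 | 0.56 / 0.89 / 0.11 | 0.564 / 0.892 / 0.108 |
| 0.42, 0.22 | 0.014 / 0.05 / 0.95 | 0.0135 / 0.051 / 0.949 |
| 0.42, 0.05 | 0.044 / 0.096 / 0.904 | 0.045 / 0.096 / 0.904 |
| 0.20, 0.22 | 0.056 / 0.21 / 0.79 | 0.057 / 0.211 / 0.789 |

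The stated table is correct for a design with no such exclusion.

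**Step 2: direction for the response rate.** Suppose (assumption) 5 confirmed responders and 2 excluded and replaced, so 31 treated. The plan reports 5/29 = 17.2%. Kept as non-responders: 5/31 = 16.1%. Counted as responders: 7/31 = 22.6%. The plan's figure lies between the two, and here 5 responders meet the final boundary either way.

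**Step 3: affected patients would otherwise fail both endpoints.** An example is a response at Cycle 2 or 4 with other therapy before the disease control time point. With u = m/29, exclusion and replacement divides every cell by 1 − u after subtracting u from the neither cell. At the null, P(S) = 0.20/(1 − u) and P(R) = 0.05/(1 − u).

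| m | P(S) | P(R) | P(effective) |
|---|---|---|---|
| 0 | 0.200 | 0.050 | 0.108 |
| 1 | 0.207 | 0.052 | 0.128 |
| 2 | 0.215 | 0.054 | 0.151 |
| 3 | 0.223 | 0.056 | 0.178 |

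**Step 4: affected patients are disease control successes with an unconfirmed response.** An example is a first PR at Cycle 6. Now u comes out of the S-only cell. At P(S) = 0.42, P(R) = 0.05 the disease control rate becomes (0.42 − u)/(1 − u).

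| m | P(S) | P(effective) |
|---|---|---|
| 0 | 0.420 | 0.904 |
| 1 | 0.399 | 0.862 |
| 2 | 0.377 | 0.803 |
| 3 | 0.353 | 0.725 |

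Step 4 requires that a patient inevaluable for response alone is dropped and replaced.

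**Step 5: handling compared at an assumed f = 25%**, with design rates taken to count observed responses. P(effective):

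| P(S), P(R) | All counted | Excluded and replaced | Kept as non-response, disease control scored | Kept as failure on both |
|---|---|---|---|---|
| 0.42, 0.22 | 0.949 | 0.890 | 0.927 | 0.840 |
| 0.20, 0.22 | 0.789 | 0.580 | 0.528 | 0.525 |

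**The case against.** - **The bias has no fixed sign.** Section 9.2 defines a response by when CR or PR is first evaluated, and the Section 9.6 numerator does not mention confirmation. Against counting observed responses the exclusion is conservative. This stands. A reader might infer that the rule simply inflates the response rate or the false-positive risk; that holds only against the confirmed standard of Section 10.2.3.3.
- **Loss of a disease control success rests on one reading.** The disease control exception ends at four months or six cycles, so a first PR at Cycle 6 is inevaluable for response only. If the replacement sentence means inevaluable on both endpoints, that patient is not replaced and the success stays. Replacement is also optional. This stands, although the Section 9.2 wording favours the broader reading.
- **Replacements are not free extra chances.** A reader might take two replacements as a 1 − 0.8² = 0.36 chance of an added disease control success at P(S) = 0.20. That ignores what was removed: at Pr(S|R) = 0.90, two responders carry 2 × 0.90 = 1.8 expected successes, and their replacements bring 2 × 0.20 = 0.4.
- **The event may be rare.** At P(R) = 0.05 only 29 × 0.05 = 1.45 responders are expected, so three affected patients near the null is an outer bound.
- **The exclusion is prespecified, and other therapy confounds the confirming scan.** Both true. Neither justifies treating this patient differently from one whose follow-up was cut short by toxicity.
- **The change could cost power.** In part. Step 5 shows a gain at (0.42, 0.22) when disease control has already been reached (0.927 against 0.890), a loss when it has not (0.840), and a loss at (0.20, 0.22) (0.528 against 0.580).

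**Conclusion.** The point holds as an outcome-dependent exclusion in Section 9.4. Apart from ineligible or undosed patients, an observed CR/PR followed by other therapy before confirmation is that section's only stated ground for inevaluability. It is not the only one in the protocol, because Section 4.1 adds one that does not depend on response.

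Its size rests on an undocumented frequency. With 1 to 3 affected patients per 29, all replaced, null P(effective) moves from 0.108 to 0.128-0.178 if they would otherwise fail both endpoints. P(effective) at (0.42, 0.05) falls from 0.904 to 0.862-0.725 if they are disease control successes and the broader reading of replacement applies. With no such patient, nothing changes.

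The documents do not support the stronger conclusions that the Section 9.2 probabilities are wrong, or that both co-primary counts are necessarily distorted. The table reproduces; it does not model this exclusion. The wording should be corrected, but the design need not be reworked.

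**What to change.** 1. Delete the CR/PR-conditioned exception from both the response and the disease control paragraphs of Section 9.4. Deleting only the first would leave a responder at Cycle 2 or 4 inevaluable for disease control.
2. Keep every eligible treated patient in both denominators, with no replacement for this event.
3. Count a CR or PR not confirmed before non-protocol anti-cancer therapy as non-response.
4. Score disease control at its own time point whether or not the response is later confirmed, and as not a success if non-protocol therapy starts before that time point.
5. Report the response rate counting unconfirmed responses as a sensitivity line.
6. State whether the replacement sentence means inevaluable on either endpoint or on both, and reconcile the evaluability statements in Sections 4.1, 9.2 and 9.4.

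The cost is wording only, with no extra patients or data. The reported response rate may be slightly lower, and the effect on power can go either way, as Step 5 shows.

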4.1 Overview of Treatment Plan

This is a single arm Phase 2 study to evaluate the use of CDX-011, an ADC directed against GPNMB. All subjects will receive CDX-011 at 1.9 mg/kg intravenously over 90 minutes every 21 days. Treatment will be discontinued if there is evidence of progressive disease or drug related toxicity that requires removal from therapy, as defined in [Section 5.0](#). Therapy may otherwise continue for a maximum duration of 14 months or ~18 cycles, whichever occurs first. Radiographic imaging assessments of disease status obtained after Cycles 2, 4 and 6 will be compared to imaging done just prior to initiating therapy. For those patients remaining on protocol therapy, subsequent imaging studies for assessment of disease status will occur after every 3rd cycle.

Other therapy: Although not encouraged, subjects who achieve a partial response after Cycle 2 that is confirmed after Cycle 6 will be allowed to undergo resection of sites of disease or radiation and remain on protocol therapy. Therapy will be held during surgery and resumed when recovered from surgery but at least 2 weeks after surgery. CDX-011 therapy will be held during radiation and may be resumed upon completion of the radiation treatment course. If the patient has not recovered from surgery within 6 weeks the patient will go off protocol therapy. Surgery or radiation performed on any site of measurable disease before the end of the sixth cycle will render the patient inevaluable for disease control assessment and they will be removed from protocol therapy.

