10.0 EVALUATION CRITERIA

10.1 Common Terminology Criteria for Adverse Events (CTCAE)

This study will utilize version 4.0 of the CTCAE of the National Cancer Institute (NCI) for toxicity and performance reporting. A copy of the CTCAE version 4.0 can be downloaded from the CTEP website

(http://ctep.cancer.gov/protocolDevelopment/electronic_applications/ctc.htm).

Additionally, toxicities are to be reported on the appropriate case report forms.

Please note: 'CTCAE v4.0' is understood to represent the most current version of CTCAE v4.0 as referenced on the CTEP website (ie, v4.02 and all subsequent iterations prior to version 5.0).

10.2

Response Criteria for Patients with Solid Tumors

For the purposes of this study, patients should be evaluated for response following Cycles 2, 4 and 6 and following every 3rd cycle thereafter. Patients who have a RECIST response (CR or PR) at Cycle 6 will have confirmatory imaging after Cycle 8.

Response and progression will be evaluated in this study using the new international criteria proposed by the revised Response Evaluation Criteria in Solid Tumors (RECIST) guideline (version 1.1).⁵¹ Changes in the largest diameter (unidimensional measurement) of the tumor lesions and the shortest diameter in the case of malignant lymph nodes are used in the RECIST criteria.

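### Section 9.4 counts a confirmed responder who later stops CDX-011 for toxicity or death as a non-responder, which contradicts Sections 9.2 and 10.2.3.3

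*Combined protocol and SAP*

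**What the plan says.** Section 9.4, on evaluability for RECIST response, states that "patients who stop CDX-011 after the 1st evaluation because of toxicities or death" are "evaluable for the response evaluation and will be counted as non-responders for the response endpoint". The sentence before it makes a patient inevaluable if non-protocol anti-cancer therapy is given "during the response evaluation period after the patient is considered as having a partial or complete response but prior to confirmation of this status".

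Section 9.2 (Design Characteristics) defines R as a RECIST CR or PR "where the first evaluation of CR or PR is made at or before the end of the sixth cycle of study therapy". It does not require the patient to stay on drug.

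Section 10.2.3.3 takes the best response from the start of treatment until progression or recurrence, provided that the measurement and confirmation criteria are met.

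Under Section 10.2, "patients should be evaluated for response following Cycles 2, 4 and 6 and following every 3rd cycle thereafter". Under Section 4.1, "Therapy may otherwise continue for a maximum duration of 14 months" or about 18 cycles. Section 8.1 lists unacceptable toxicity as a reason to leave therapy.

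At the end of stage II, Section 9.2 declares sufficient activity with "9 or more disease control successes or 5 or more RECIST responders". The numerator of P(R) in Section 9.6 is "Number of Patients Considered as PR or CR".

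**The concern.** Take a patient with a PR after Cycle 2 that is confirmed after Cycle 4 and who stops for toxicity in Cycle 5. Sections 9.2 and 10.2.3.3 make this patient a responder. Section 9.4, read as written, makes the same patient a non-responder. Because the sentence has no end date, a stop in Cycle 15 has the same effect.

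Response is one of two routes to a positive result and is decided on small counts. Recoding one patient turns 5/29 into 4/29, which makes the trial negative if disease control successes are 8 or fewer. At stage I it turns 2/19 into 1/19, which stops the trial if disease control successes are 4 or fewer. The reported response rate falls by 1/29 = 3.4 percentage points for each such patient. Two analysts could score the same patient differently, and the question might first be raised when the outcomes are already known.

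**Working it through.** **Does another part of the plan resolve the conflict?**

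- The first evaluation in 9.4 is not defined. It could be the scan after Cycle 2, or the first evaluation of CR or PR in the sense of 9.2. Neither reading exempts a confirmed response.
- The numerator in 9.6 fits either scoring.
- For disease control, 9.4 limits its rule on treatment-related death to the first six cycles and first four months. The response sentence has no such limit.
- A patient who stops before confirmation is a non-responder under 10.2.3.3 as well. The conflict is therefore confined to responses already confirmed.

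**Inputs from Section 9.2.** Stage I has n = 19 and stops if S ≤ 4 and R ≤ 1, where S is the number of disease control successes and R the number of responders. Stage II adds n = 10, and the trial is negative if cumulative S ≤ 8 and R ≤ 4. Pr(S|R) = 0.90.

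**Method.** Each patient falls into one of four cells, where P(S and R) = 0.90 × P(R) and the other cells follow from P(S) and P(R). The joint distribution of (S, R) was enumerated exactly over both stages.

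**The plan's own figures.** The probability of concluding the drug is effective is reproduced in all four rows:

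| P(S) / P(R) | Stated | Computed |
|---|---|---|
| 0.20 / 0.05 | 0.11 | 0.108 |
| 0.42 / 0.22 | 0.95 | 0.949 |
| 0.42 / 0.05 | 0.904 | 0.904 |
| 0.20 / 0.22 | 0.79 | 0.789 |

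**Effect of the 9.4 sentence.** Let q be the share of responders recoded as non-responders, with S unchanged, so that P(R) becomes P(R) × (1 − q). For example, 0.22 × 0.90 = 0.198. The documents do not give q, so the values below are assumptions.

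| P(S) / P(R) | q = 0 | q = 5% | q = 10% | q = 20% |
|---|---|---|---|---|
| 0.20 / 0.22 | 0.789 | 0.746 | 0.698 | 0.588 |
| 0.42 / 0.22 | 0.949 | 0.945 | 0.940 | 0.931 |
| 0.42 / 0.05 | 0.904 | 0.904 | 0.904 | 0.903 |
| 0.20 / 0.05 | 0.108 | 0.107 | 0.106 | 0.104 |

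Losing responders can only turn a positive decision negative. Each fall is therefore the probability that the decision changes. In the 0.20/0.22 row this is 4.3%, 9.0% and 20.0%.

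If the stops come after the stage I decision, so that only the final count is recoded, the 0.20/0.22 row becomes 0.748, 0.702 and 0.594, which is nearly the same.

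**Intermediate disease control, P(R) = 0.22, q = 10%.** P(S) = 0.25: 0.791 to 0.708. P(S) = 0.30: 0.816 to 0.757. P(S) = 0.35: 0.871 to 0.839.

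**One patient from reversal.** The chance of ending with exactly 5 responders and 8 or fewer disease control successes is 15.2% at 0.20/0.22 and 1.6% at 0.42/0.22.

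**Scale for q.** If the risk of a toxicity or death stop is h per cycle over n cycles after confirmation, q = 1 − (1 − h)^n. A response confirmed after Cycle 4 has at most 18 − 4 = 14 further cycles. There, q = 5%, 10% and 20% correspond to h = 0.37%, 0.75% and 1.6%. With only 4 further cycles they correspond to h = 1.3%, 2.6% and 5.4%.

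**The case against.** The strongest reply is that the passages can be read together. The sentence follows one about the period before confirmation. If the first evaluation means the first evaluation of CR or PR, the rule covers a patient who stops between first response and confirmation, and scoring that patient as a non-responder agrees with 10.2.3.3. If it means the first scan, its likely purpose is to keep toxicity dropouts in the denominator. A response that could be revoked until about Cycle 18 would also leave the counts open long after the staged decision needs them. This narrower intent is likely, and the Cycle 15 case is the less plausible one. But the restriction is not written, and the Cycle 5 case does not need the long window.

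The second reply is that 0.22 might already be net of the recoding, in which case the design table stands. That does not fit 9.2, which defines R without any such recoding.

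The third reply concerns size, and much of it stands. The value of q has no source in the documents, and at q = 10% with P(R) = 0.22 only about 29 × 0.22 × 0.10 = 0.6 patients are recoded. The 0.20/0.22 row is also a corner case: P(S and R) = 0.198, so only 0.2% of patients have disease control without response. If non-responders had the historical 12% four-month EFS of Section 2.1 (an assumption), P(S) would be 0.198 + 0.12 × 0.78 ≈ 0.29, and q = 10% would lower the probability from 0.809 to 0.746. The loss is smaller but still real.

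**Conclusion.** The concern holds. Read as written, 9.4 miscodes one component of the primary endpoint for confirmed responders who later stop for toxicity or death, and no other section reconciles it with 9.2 and 10.2.3.3.

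The bias in P(R) is downward, the false-positive rate does not rise, and disease control scoring is untouched. The loss of power is material where response is high and disease control low to moderate. It is small at 0.42/0.22, at most 1.8 percentage points for q up to 20%, and negligible at P(R) = 0.05. All these sizes depend on the assumed q and on disease control being unchanged by the recoding. The textual conflict depends on neither.

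It should be fixed. Section 9.2 treats P(R) of at least 0.22 as sufficient for promotion by itself, and 0.20/0.22 is already the alternative with the lowest power in the design table.

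**What to change.** Amend the sentence in 9.4 along these lines:

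> Patients who stop CDX-011 because of toxicity or death are evaluable for response. They count as non-responders unless a CR or PR was first documented at or before the end of Cycle 6 (Section 9.2) and met the confirmation criteria (Section 10.2.3.3). Such a CR or PR remains a response whatever happens later to treatment.

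This removes the undefined first evaluation from the rule and keeps unconfirmed responders who stop as non-responders. Add a cross-reference in the definition of R in 9.2 and in the numerator of P(R) in 9.6.

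If the intention is to count confirmed responders who later stop for toxicity or death as failures, state that in the definition of R in 9.2, so that 0.05 and 0.22 refer to that endpoint.

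The cost is one or two sentences and two cross-references. Sample size, decision rule, scans and data collection do not change.
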